8.3.3.2 Specimen Shipment

Specimen shipment will occur at intervals during the trial following all applicable International Air Transport Association (IATA) requirements and according to the specifics for storage temperature and documentation as detailed in the central clinical laboratory manual and protocol-specific MOP, as appropriate.

All specimens for clinical screening and safety laboratory evaluations will be transported from the CTU to the local clinical laboratory.

Plasma samples for bioanalytical assays will be shipped from the CTU to DMID-CMS at:

Fisher BioServices
c/o DMID Clinical Materials Services (CMS)
[name]
[name]
[contact]
[contact]
Email: [contact]

Plasma samples will then be provided by DMID-CMS to the bioanalytical lab, KCAS Inc., at:

KCAS Bioanalytical Services
c/o [name], Senior Manager, PBI
[name]
[name]
Office: [contact]
Email: [contact]

9 ASSESSMENT OF SAFETY

Regulatory requirements including FDA regulations and ICH Guidelines for GCP set forth safety monitoring and reporting responsibilities of sponsors and investigators to ensure the safety and protection of human subjects participating in clinical trials.

Responsibilities:

Investigators participating in this clinical trial are responsible for and will:

- Evaluate subject safety including assessment of AEs for seriousness, severity, and causality (relatedness to study drug);
- Notify DMID of SAEs within 24 h of site awareness;
- Provide detailed written reports, including necessary documentation requested by DMID or IRB/EC, promptly following immediate initial reports;
- Inform the IRB/EC of SAEs and AEs as required by applicable regulatory requirements.

9.1 Specification of Safety Parameters

Safety will be assessed by the timing, frequency, causality, and severity of:

1. Treatment-emergent SAEs occurring from time of first dose in dosing period 1 through Final Visit (Day 8 \pm 2 after last dose in dosing period 4), or ET;
2. Clinical laboratory AEs occurring from time of first dose in dosing period 1 through Final Visit (Day 8 \pm 2 after last dose in dosing period 4), or ET;
3. Non-serious, unsolicited treatment-emergent AEs occurring from time of first dose in dosing period 1 through Final Visit (Day 8 \pm 2 after last dose in dosing period 4), or ET.

9.2 Methods and Timing for Assessing, Recording, and Analyzing Safety Parameters

9.2.1 Adverse Events

Definitions

ICH E6 defines an AE as any untoward medical occurrence in a subject or clinical investigation subject who was administered a pharmaceutical product, regardless of its causal relationship to the product. An AE can therefore be any unfavorable and unintended sign (including an abnormal laboratory finding), symptom, or disease temporally associated with use of the product. The occurrence of an AE may come to the attention of study personnel during study visits and interviews, or by a subject presenting for medical care.

The FDA defines an AE as any untoward medical occurrence associated with the use of a drug in humans, whether it is considered drug-related or not.

Any medical condition that is present at the time that the subject is screened will be considered a baseline finding and not reported as an AE. However, if the condition increases in severity or frequency at any time during the trial, it will be recorded as an AE.

All AEs will be graded for severity and relationship to the study drug.

9.2.1.1 Severity of Events

Intensity of AEs will be graded as follows, unless otherwise specified in [Appendix C](#):

Mild: Require minimal or no treatment; do not interfere with the subject's daily activities.

Moderate: Result in a low level of inconvenience or concern with therapeutic measures; may cause some interference with functioning.

Severe: Interrupt a subject's usual daily activity and may require systemic drug therapy or other treatment; are usually incapacitating.

9.2.1.1.1 Relationship to Study Products

AEs and SAEs will be assessed by the investigator to determine relationship to the study drug, using the following two terms. In a clinical trial, the study drug must always be suspect.

- **Related:** There is a reasonable possibility that the study drug caused the AE/SAE
- **Not Related:** There is not a reasonable possibility that the study drug caused the AE/SAE

The investigator will provide an assessment of association or relationship of each AE/SAE to the study drug based on:

- Temporal relationship of the AE/SAE to study drug dosing;
- Whether an alternative etiology has been identified;
- Biological plausibility;
- Existing therapy and/or ConMeds.

9.2.1.2 Reporting Adverse Events

AEs will be captured on the appropriate subject's source document and eCRF. Information collected for AEs includes event description, time of onset, investigator assessment of severity and relationship to the study drug, date of resolution of the event, seriousness, and outcome.

All AEs will be documented from the time of study drug dosing through Final Visit. AEs will be followed to resolution or until considered stable in the clinical judgment of the study investigator. Evaluation of AEs may require unscheduled visits and clinical and laboratory investigations, according to the clinical judgment of the Site PI and study physicians.

9.2.2 Serious Adverse Events

An SAE is any AE that meets at least one of the following criteria:

- Death;
- Life-threatening AE*;
- Inpatient hospitalization or prolongation of existing hospitalization;
- Persistent or significant disability or incapacity, or substantial disruption of the ability to conduct normal life function;
- Congenital anomaly/birth defect;
- Important medical events that may not result in death, be life-threatening, or require hospitalization may be considered an SAE when, based upon appropriate medical judgment, they may jeopardize the subject and may require medical or surgical intervention to prevent one of the outcomes listed in this definition. Examples of such medical events include allergic bronchospasm requiring intensive treatment in an emergency room or at home, blood dyscrasias or convulsions that do not result in inpatient hospitalization, or the development of drug dependency or drug abuse.

*An AE is considered “life-threatening” if, in the view of either the investigator or DMID, its occurrence places the subject at immediate risk of death. It does not include an AE that, had it occurred in a more severe form, might have caused death.

SAEs will be:

- Assessed for severity and relationship to study product and alternate etiology by an authorized study physician (listed on FDA Form 1572);
- Recorded on the appropriate SAE data collection form and eCRF;
- Followed through resolution;
- Reviewed and evaluated by an ISM (as deemed necessary), the SMC (periodic review unless related), DMID, and the IRB.

9.2.3 Procedures to be Followed in the Event of Abnormal Laboratory Test Values or Abnormal Clinical Findings

A licensed study clinician (listed on FDA Form 1572) will determine seriousness, severity, and causality; provide a medical evaluation of AEs; and classify AEs based upon medical judgment.

Abnormal laboratory values or clinical findings for all enrolled subjects after dosing will be assessed using the toxicity scales in [Appendix C](#). Abnormal values and findings noted at screening or baseline will only be considered AEs if they deteriorate after study drug dosing. For abnormalities noted from the time of first study drug dosing, any Grade 1 or higher laboratory abnormality listed on the toxicity table in [Appendix C](#) will be entered in the database as an AE. Safety laboratory results that are abnormal according to the local laboratory reference range, but not considered Grade 1 abnormalities, will be evaluated by the CTU clinician and reported as Grade 1 abnormalities if clinically significant. If not clinically significant, these will not be considered laboratory AEs and thus will not be graded but will be recorded in the source document and followed-up clinically at the discretion of the CTU clinician. Abnormal laboratory

values, performed as part of HEM, CHEM, or UA but not listed in this toxicity table will be evaluated by the study clinicians, recorded in the source document and, if clinically significant, considered AEs and graded according to the criteria in [Section 9.2.1](#).

Protocol-specific laboratory normal range values in effect at the time of protocol submission are included in [Appendix B](#). Changes in these ranges during the trial will be handled as administrative protocol amendments and toxicity grades will be calculated using the new ranges from the effective date of the change. A regular protocol amendment will be submitted for these changes if a revised laboratory normal range value meets criteria for Grade 2 toxicity.

Gross blood in urine that is confirmed due to menses is not an AE (but is for all other reasons).

9.3 Reporting Procedures

9.3.1 Serious Adverse Events

SAEs will be followed until resolution even if this extends beyond the study-reporting period. Resolution of an AE is defined as the return to pretreatment status or stabilization of the condition with the expectation that it will remain chronic.

All SAEs will be:

- Recorded on the appropriate SAE report form and sent to DMID Pharmacovigilance Group (PVG)
- Entered into the appropriate subject source document and eCRF in AdvantageEDCSM
- Reported to the Site ISM and the IRB
- Reviewed and followed to resolution or stability by an authorized study physician (listed on FDA Form 1572)
- Collected on each subject until Final Visit or ET Visit

Any AE that meets a protocol-defined serious criterion will be submitted immediately (within 24 h of site awareness) on an SAE report form to DMID PVG:

DMID Pharmacovigilance Group
Clinical Research Operations and Management Support (CROMS)
[name]
[name]
SAE Hot Line: [name] (US) or [name] (outside US)
SAE [contact] (US) or [name] (outside US)
SAE Email Address: [contact]

In addition to the SAE report form, selected SAE data fields will also be entered into AdvantageEDCSM. Please see the protocol-specific MOP for details regarding this procedure.

Other supporting documentation of the SAE may be requested by DMID PVG and will be provided as soon as possible.

The CTU will copy the ISM on SAE reports provided to the DMID PVG. The DMID Medical Monitor (MM) and DMID CPM will be notified of the SAE by the DMID PVG. The DMID MM will review and assess the SAE for regulatory reporting and potential impact on subject safety and protocol conduct.

At any time after completion of the trial, if the Site PI or appropriate sub-investigator becomes aware of an SAE that is suspected to be related to study drug, the Site PI or appropriate sub-investigator will report the event to the DMID PVG.

9.3.2 Regulatory Reporting for Studies Conducted Under DMID-Sponsored IND

Following notification from the investigator, DMID, the Investigational New Drug (IND) sponsor, will report any suspected AE that is both serious and unexpected. DMID will report an AE as a suspected AE only if there is evidence to suggest a causal relationship between the drug and the AE. DMID will notify FDA and all participating investigators (i.e., all investigators to whom DMID is providing drug under its IND(s) or under any PI's IND(s)) in an IND safety report of potential serious risks from clinical trials or any other source, as soon as possible, but in no case later than 15 calendar days after DMID determines that the information qualifies for reporting as specified in 21 CFR Part 312.32. DMID will also notify FDA of any unexpected fatal AE or suspected life-threatening AE as soon as possible, but in no case later than 7 calendar days after DMID's initial receipt of the information. Relevant follow up information to an IND safety report will be submitted as soon as the information is available. Upon request from FDA, DMID will submit to FDA any additional data or information that the agency deems necessary, as soon as possible, but in no case later than 15 calendar days after receiving the request.

All serious events designated as "not related" to the study drug will be reported to the FDA at least annually in a summary format.

9.3.3 Other Adverse Events (if applicable)

9.3.3.1 Reporting of Overdose

An overdose is defined as a dose greater than the high-dose level evaluated in the trial as described in [Section 6.3.1](#) of the protocol. All overdoses will be reported; if the overdose is associated with an AE, then the AE will also be reported. In the event of an overdose of study drug, the investigator will use clinical judgment in treating the overdose and contact the DMID MM. The investigator will refer to the relevant document(s) for detailed information regarding warnings, precautions, contraindications, AEs, and other significant data pertaining to zoliflodacin. Such documentation may include but not be limited to the IB.

9.3.4 Reporting of Pregnancy

Pregnancies that occur in female subjects during the trial will be reported via AdvantageEDCSM on a pregnancy report form. With the subject's permission, all protocol-required venous blood samples will be obtained, and the subject will continue to be followed for safety until Final Visit. Efforts will be made to follow all pregnancies reported during the trial to pregnancy outcome, as described in the protocol-specific MOP (e.g., delivery, spontaneous abortion, or therapeutic abortion), pending the subject's permission.

A female subject who participates in the trial and becomes pregnant will be asked to inform study personnel of a pregnancy occurring 30 days after Final Visit. A male subject who participates in the trial and whose female partner becomes pregnant from the time of first dosing to 90 days after Final Visit will be asked to inform study personnel of the pregnancy. For all reported pregnancies, subjects will be asked to provide pregnancy outcome upon delivery or pregnancy termination to the CTU.

9.4 Type and Duration of Follow-up of Subjects after Adverse Events

Treatment-emergent SAEs and AEs will be followed until resolution or until considered stable in the clinical judgment of the investigator. Resolution of an AE is defined as the return to pretreatment status or stabilization of the condition in the clinical judgment of the study investigator, with the expectation that it will remain chronic.

Follow-up procedures, evaluations, and outcomes will be recorded in the subject's source document and eCRF.

9.5 Halting Rules

9.5.1 Study Halting Criteria

9.5.1.1 Halting Criteria for Zoliflodacin and Placebo Periods

Study dosing of zoliflodacin or placebo will be temporary halted, and a review of available safety data will be conducted by the SMC if any of the following occur after dosing:

1. Death of a subject following dosing regardless of relatedness to the study drug;
2. One subject with a non-fatal SAE that is considered related to the study drug by the study PI or authorized physician (listed in FDA Form 1572);
3. Two or more subjects experience a QTcF >500 msec or ≥ 60 msec above baseline, based on readings from at least two standard 12-lead ECGs after study drug administration;
4. Two or more subjects with a Grade 3 systemic AE coded in the same organ system that is considered related to the study drug by the study PI or authorized clinician;

Note: VS abnormalities will be considered part of a systemic disorder or an organ-specific condition, as described in Appendix C: Adverse Events Toxicity Grading Criteria

, in order to be included among the Study Halting Criteria.

5. One subject experiences a symptomatic ventricular tachyarrhythmia with or without QTcF prolongation after study drug administration;
6. An overall pattern of symptomatic, clinical non-serious events that may appear minor in terms of individual events, but that may collectively represent a serious potential safety concern and pose a risk to continuing a subject in the trial.

9.5.1.2 Halting Criteria for Moxifloxacin Periods

Study dosing of moxifloxacin will be temporary halted, and a review of available safety data will be conducted by the SMC if any of the following occur after dosing:

1. Death of a subject following dosing regardless of relatedness to moxifloxacin;
2. One subject with a non-fatal SAE that is considered related to moxifloxacin by the study PI or authorized physician (listed in FDA Form 1572);
3. Three or more subjects with a Grade 3 systemic AE coded in the same organ system that is considered related to moxifloxacin by the study PI or authorized clinician.

Note: VS abnormalities will be considered part of a systemic disorder or an organ specific condition, as described in Appendix C: Adverse Events Toxicity Grading Criteria
, in order to be included among the Study Halting Criteria.

9.6 Safety Oversight

9.6.1 Independent Safety Monitor (ISM)

The ISM is a physician with relevant expertise whose primary responsibility is to provide independent safety monitoring in a timely fashion. The ISM will review SAEs and other AEs as needed and provide an independent assessment to DMID.

9.6.2 Safety Monitoring Committee (SMC)

Safety oversight will be conducted by a SMC, which is an independent group of experts that monitors subject safety and advises DMID. SMC members will be separate and independent of study personnel participating in the trial and will not have scientific, financial, or other conflicts of interest related to the trial. The SMC will consist of members with appropriate expertise to contribute to the interpretation of the data from the trial.

The SMC will meet as follows:

- Organizational meeting (before study initiation)
- *Ad hoc* meeting
 - When study halting criteria are met
 - At the request of DMID to review a potential safety concern identified by either the Site PI, ISM, or DMID MM
- Scheduled meeting

- The SMC will review cumulative, unblinded interim safety data when available after database lock

Procedures for SMC reviews/meetings will be defined in the SMC charter. The SMC will review safety data and advise on resumption or stopping of a temporary halted trial, and safety monitoring in future clinical trials with zoliflodacin.

10 CLINICAL MONITORING

10.1 Site Monitoring Plan

Site monitoring will be conducted to ensure that human subject protections, study and laboratory procedures, study intervention administration, and data collection processes are of high quality and meet DMID, GCP/ICH, and regulatory guidelines, when appropriate. Site visits may be conducted by an authorized representative of DMID or other regulatory agencies to inspect study data, subjects' medical records, and eCRFs in accordance with ICH guidelines, GCP, and the respective local and national government regulations and guidelines.

The investigator will permit authorized representatives of DMID and the respective local and national health authorities to inspect facilities and records relevant to the trial, if needed.

A separate monitoring plan developed by DMID will describe protocol-specific items to be monitored.

Site visits will be made at standard intervals defined by DMID and may be made more frequently as directed by DMID. Monitoring visits will include, but not be limited to, review of regulatory files, accountability records, subjects' source documents, eCRFs, ICFs, clinical and laboratory reports, and protocol and GCP compliance. Site monitors will have access to the CTU, study personnel, and all study documentation according to the DMID-approved site monitoring plan. Study monitors will meet with the Site PI to discuss any problems and actions to be taken and document visit findings and discussions.

11 STATISTICAL CONSIDERATIONS

11.1 Study Hypotheses

The trial will evaluate the following hypotheses:

- a. Zoliflodacin administered at 2-g or 4-g doses causes a prolongation of the QTcF interval that exceeds the criteria in the ICH Guidance E14.¹⁶

(A negative effect is defined in ICH Guidance E14 as “one in which the upper bound of the one-sided 95% confidence interval (CI) for the largest time-matched mean effect of the drug on the QTcF interval is <10 msec.”)

- b. The trial has the sensitivity to detect an effect on QTcF of regulatory concern, as produced by moxifloxacin.

(Assay sensitivity will be demonstrated if, for at least one individual timepoint between 1h and 4h after administration of moxifloxacin, the lower bound of the one-sided 95% CI for $\Delta\Delta\text{QTcF}$, is >5 msec.)

11.2 Sample Size Considerations

Enrollment of 72 subjects would provide at least 84% power to conclude a negative effect, given that up to 16 subjects may withdraw early prior to beginning to replace subjects (at least 56 subjects evaluable), and assuming a standard deviation of $\Delta\Delta\text{QTcF}$ of 7 msec and an underlying effect of 5 msec.

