Regulatory guidance has emphasized the need to obtain clear robust data on the effect of new chemical entities on ECG parameters with focus on cardiac repolarization as measured by the corrected QT interval (QTc) duration.¹⁶ Though many Phase 1, 2, and 3 studies may be conducted, they usually have insufficient sample size, infrequent sampling of ECG data, or the use of inadequate controls to overcome the high rate of spontaneous change in QTc duration.

This has resulted in regulatory guidance recommending a dedicated TQT study to define the ECG effects of new drugs.¹⁶

Therefore, this four-arm crossover trial will include therapeutic and suprathreshold dosing with zoliflodacin, placebo as a negative control, and oral moxifloxacin as a positive control. The trial will be conducted in accordance with relevant ICH E14 and Food and Drug Administration (FDA) guidance.¹⁶

The positive control (moxifloxacin) will serve to validate the sensitivity of the assay to detect small increases from baseline in the QTc interval corrected using Fridericia's formula (QTcF). Moxifloxacin will be used because it has been demonstrated to increase QTc by a mean of 6 msec (time-averaged analysis: standard deviation (SD) = 26 msec; N = 787) after a 400-mg oral dose.^{16,18} However, thorough ECG studies have shown that this dose of moxifloxacin can be expected to show, for a time-matched analysis, a mean change of 10-15 msec, generally within 1-6 h after dosing.¹⁹

This trial will be performed in healthy subjects to eliminate variables known to change ECG parameters (e.g., concomitant drugs or diseases) among subjects. The sample size is driven by the need to do a time-matched statistical analysis on the primary endpoint as per ICH E14 guidance. A crossover study design was chosen so that subjects will act as their own controls. A crossover trial can be conducted since the half-life of zoliflodacin is approximately 6 h. A wash-out phase of 8 ±2 days after Day 1 of each dosing period is considered sufficient to prevent a carryover effect of the study drug between treatments.

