4 STUDY DESIGN

The TQT study will be performed in a single center, the Vince & Associates Clinical Research, Inc., clinical trials unit (CTU), according to a randomized, double-blinded (except for the use of moxifloxacin), placebo-controlled, four-period, four-treatment, crossover design balanced with respect to first-order carryover effect in 72 healthy male or female subjects, aged 18 to 45 years inclusive, to evaluate the effect of zoliflodacin on QTcF and other ECG parameters, the correlation of the drug concentrations (and PK profile) with $\Delta\Delta\text{QTcF}$, and the PK and safety profiles of the new zoliflodacin formulation.

Subjects who consent to participate will be enrolled in the trial if they meet all inclusion and no exclusion eligibility criteria. Laboratory assessments at Screening Visit will include routine clinical laboratory tests (HEM, CHEM, and UA), testing for viral serology (HIV antibody, HBsAg, and HCV antibody), drugs of abuse, and alcohol. Serum pregnancy testing will be done in all women and serum FSH levels will be measured only in post-menopausal women.

Each subject will receive one dose of each of four treatments, labeled A through D:

- Treatment A: zoliflodacin 2 g PO (investigational drug, therapeutic dose)
- Treatment B: zoliflodacin 4 g PO (investigational drug, supratherapeutic dose)
- Treatment C: placebo PO (for zoliflodacin 4 g)
- Treatment D: moxifloxacin 400 mg PO (positive control comparator)

In the dosing phase, each subject will be randomly allocated to one of 12 dosing sequences before dosing on Day 1, Dosing Period 1, and receive a single dose of the following four study drugs on different days according to their randomly-assigned dosing sequence, as follows:

Table 1: Dosing Sequences

ABCD	ACDB	ADBC
BADC	BDCA	BCAD
CDAB	CABD	CBDA
DCBA	DBAC	DACB

Six of the planned 72 subjects will be included in each treatment sequence. The design is balanced for period and first-order carryover effects.

Subjects will be dosed in the morning of Day 1 in each dosing period, in a staggered fashion at least several minutes apart, and will receive study drug at approximately the same time in each

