5.3.4 Handling of Withdrawals and Discontinuation of Administration

- Subjects who are withdrawn before dosing may be replaced with a subject assigned the same sequence.
- A subject who cannot ingest the entire 60 mL volume of zoliflodacin or placebo suspension or a subject who took the entire dose but vomits up to 5 h after dosing with zoliflodacin or placebo or moxifloxacin will be withdrawn from data analysis for the period when the event occurred, but will not be withdrawn from the trial and may complete the remaining treatment periods in the assigned dosing sequence.
- Subjects who ingest the entire volume of the initial 60-mL drug suspension but who do not ingest the content of the second 60-mL rinse will not be withdrawn from the trial.
- Subjects who withdraw after receiving at least one treatment in a treatment sequence will not be replaced, unless more than 16 subjects withdraw from the trial.
- Subjects who received any amount of the study drug but withdraw from the trial within 24 h after dosing will be encouraged to continue follow-up (with subjects' consent) for safety assessments and PK sample collection.
- Subjects withdrawing will be asked to complete an ET Visit if they do not wish to be followed per protocol.

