11.4.6.2 Primary Analysis: QTcF Effect

The primary hypothesis to be tested is that following administration of zoliflodacin 2 g and 4 g, the upper bound of the one-sided 95% CI of treatment effect on $\Delta\Delta\text{QTcF}$ is ≥ 10 msec for at least one of the ECG assessments, against the alternative hypothesis that all mean effects are < 10 msec.

The primary analyses will be conducted to evaluate the effects of zoliflodacin 2 g and 4 g on cardiac repolarization as measured by ΔQTcF relative to placebo. Analysis will be performed using a linear mixed model with $\Delta\Delta\text{QTcF}$ as the dependent variable, with baseline QTcF, sequence, period, treatment, time (categorical), and interactions of time with treatment as fixed

effects, and subject nested within sequence as random effects. At each of the 9 post-baseline timepoints and for each zoliflodacin dose, a one-sided 95% CI for the treatment effect on $\Delta\Delta\text{QTcF}$ will be estimated using least square means. There will be 18 CIs, one for each combination of zoliflodacin dose and timepoint. A negative effect of 2 g or 4 g zoliflodacin will be concluded if the maximum of the 18 one-sided 95% CI upper bound is <10 msec. No adjustment will be made for multiplicity, since it is not required under intersection-union testing, as planned for the trial. No subgroup analyses are planned.

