5.4. Analysis of Central Tendency (By-timepoint Analysis)

By-timepoint analysis will be performed using Holter ECG data from subjects in the Holter ECG Analysis Population. Absolute values, change-from-baseline and time-matched, placebo-corrected, change-from-baseline values for each ECG parameter will be considered for this analysis (Refer to DMID 16-0110_ECG_Table shells: Tables 3, 4 and 5; DMID 16-0110_ECG_Listing shells: Listings 1 to 7; DMID 16-0110_ECG_Figure shells: Figure 1 to 56). Change-from-baseline QTcF (Δ QTcF) values (and other ECG parameters QTcB, HR

[calculated from RR], RR, QT, PR and QRS duration values) will be calculated by subtracting the mean value of replicate ECGs at baseline from the mean value of replicate ECGs at post-dose timepoints.

Time-matched, placebo-corrected, change from baseline in QTcF interval ($\Delta\Delta\text{QTcF}$) values (and other ECG parameters QTcB, HR [calculated from RR], RR, QT, PR and QRS duration values) will be calculated as differences between time-matched change-from-baseline QTcF values for active treatment minus time-matched change-from-baseline QTcF values for placebo for each subject (Refer to DMID 16-0110_ECG_Table shells: Table 5; DMID 16-0110_ECG_Listing shells: Listings 1 to 7).

As a primary analysis, a repeated measurement analysis on $\Delta\Delta\text{QTcF}$ values will be performed at each post-dose timepoint using analysis of covariance (ANCOVA) (Refer to DMID 16-0110_ECG_Table shells: Table 6; DMID 16-0110_ECG_Figure shells: Figure 57). Unless otherwise specified, a restricted maximum likelihood based, linear mixed effect model will be used. Model will include $\Delta\Delta\text{QTcF}$ as the dependent variable. Baseline QTcF value as continuous covariate and sequence, period, treatment, nominal timepoint (as categorical) and interactions of timepoint with treatment will be treated as fixed effects. The model will also include subject nested within sequence as a random effect. SAS PROC MIXED will be used to perform the analysis.

At each of the 9 post-dose timepoints and for each zoliflodacin dose, a one-sided 95% CI for the treatment effect on $\Delta\Delta\text{QTcF}$ will be estimated using least square (LS) means. There will be 18 CIs, one for each combination of zoliflodacin dose and timepoint. A negative effect of 2 g or 4 g zoliflodacin will be concluded if the maximum of the 18 one-sided 95% CI upper bounds is <10 msec. No adjustment will be made for multiplicity.

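### The stated power of at least 84% does not match its inputs as labelled, which give at least 99.7% for the full 18-bound rule; either the power or the SD label is misstated

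*Protocol*

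**What the plan says.** Protocol 11.2 states that "Enrollment of 72 subjects would provide at least 84% power to conclude a negative effect", on the basis that "up to 16 subjects may withdraw early prior to beginning to replace subjects (at least 56 subjects evaluable"), "assuming a standard deviation of $\Delta\Delta\text{QTcF}$ of 7 msec", and taking the underlying effect as 5 msec. SAP section 5 repeats the sentence without adding to it.

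The conclusion being powered is defined in Protocol 11.4.6.2: a negative effect "will be concluded if the maximum of the 18 one-sided 95% CI upper bound is" below 10 msec. The 18 bounds come from two zoliflodacin doses and nine post-dose timepoints. The ECG SAP (SAP Appendix 4), section 5.4, uses the same rule. It defines ΔΔQTcF within the subject, as the change from baseline on active treatment "minus time-matched change-from-baseline QTcF values for placebo for each subject".

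Neither document gives the formula, the number of bounds covered, a correlation between bounds, or a source for the 7 msec. The ECG SAP has no power section.

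**The concern.** With 56 paired differences and an SD of 7 msec, a true effect of 5 msec lies more than five standard errors below the 10 msec margin. Power in the mid-80s is not what such inputs produce, even for 18 simultaneous bounds. Something in the sentence differs from the calculation behind it: the power, the meaning of the SD, the formula, or the number of bounds.

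This is the only quantitative power statement in the plan. The choice of 72 has other supports: Protocol 2.2.1 says "The sample size is driven by the need to do a time-matched statistical analysis on the primary endpoint", and Protocol section 4 says "Six of the planned 72 subjects will be included in each treatment sequence", which fixes a multiple of 12. The replacement rule in Protocol 5.3.4, under which subjects who leave after dosing "will not be replaced, unless more than 16 subjects withdraw from the trial", has no other numerical support. If losses approach 16, a reader needs to know whether 56 subjects give near-certain power or a figure that depends on an unstated correlation.

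**Working it through.** **Inputs.** Evaluable n = 72 − 16 = 56, SD 7 msec, true effect 5 msec (Protocol 11.2). Margin 10 msec, one-sided 95% bounds, 18 of them, no multiplicity adjustment (Protocol 11.4.6.2). Within-subject differences (ECG SAP 5.4). The effect is taken as 5 msec at every dose and timepoint, the worst case for that input. Per-timepoint t bounds stand in for the planned mixed model.

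**Step 1. The plan's figure from the inputs as labelled.**

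- SE = 7/√56 = 0.935 msec.
- Noncentrality = (10 − 5)/0.935 = 5.35, with 55 df.
- Power for one bound (noncentral t) = 0.99986.
- All 18 bounds, valid under any correlation: at least 1 − 18 × (1 − 0.99986) = 0.9975.

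The 84% is not reproduced; the labelled inputs give nearly 16 points more. By the same formula, 34 evaluable subjects already assure 86.5% for all 18 bounds, and 33 give 83.97%.

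**Step 2. Readings that do give about 84%.**

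| Reading | Calculation | Power | Conflict with the plan |
|---|---|---|---|
| Two parallel groups of 28, one bound | SE = 7√(2/28) = 1.871; noncentrality 2.67; 54 df | 84.0% | Ignores the crossover pairing; covers 1 bound of 18 |
| 7 msec as per-treatment SD of ΔQTcF, one dose's 9 bounds | SE = 7√(2/56) = 1.323; noncentrality 3.78; per bound 98.16% (55 df) or 98.26% (110 df); floor 1 − 9(1 − p) | 83.4% or 84.4% | Contradicts the SD label; covers one dose |
| Same SD, all 18 bounds, common correlation 0.5 | SD of ΔΔQTcF = 7√2 = 9.90; simulation | 84.0% | Contradicts the SD label; needs an unstated correlation |

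The list is not exhaustive, and nothing in the documents identifies the source.

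**Step 3. What follows if 7 msec is a per-treatment SD.** Assume periods are independent given the subject, so the SD of ΔΔQTcF is 9.90. Both doses are compared with the same placebo period. Each difference has variance 2σ² and the two share the placebo variance σ², so the doses correlate at σ²/2σ² = 0.5 at each timepoint. Simulated power for all 18 bounds, n = 56, by within-period correlation between timepoints:

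| Timepoint correlation | 18-bound power |
|---|---|
| 0 | about 73% |
| 0.5 | about 82% |
| 0.6 | about 84% |
| 0.8 | about 89% |

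On this reading 84% is reached only at a correlation of about 0.6 or more.

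**The case against.** The strongest reply is that a figure of at least 84% is true when the actual power exceeds 99%, so the sentence is a cautious lower bound and not an error. That stands as far as it goes: the sentence is not false on its labelled inputs. It does not explain why this bound was printed beside inputs that exceed it so widely.

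A second reply is that the per-treatment reading is conjecture. Protocol 11.2 and SAP section 5 both label the SD as that of ΔΔQTcF, and the abbreviation lists define ΔΔQTcF as placebo-corrected. That also stands. The reading is one candidate among several and cannot be shown to be the source. It matters because it is the case in which the printed assurance would depend on something unstated.

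A reader might go further and infer that the trial is underpowered. The documents do not support that: on the inputs as printed, power is at least 99.7% and the allowance of 16 withdrawals is more than safe. A reader might also apply the any-correlation floor to the per-treatment SD, 1 − 18(1 − p), and obtain 67% to 69%. That floor ignores the placebo period that both doses share; under the same independence assumption, power is about 73% even with uncorrelated timepoints. The timepoints within a period also share one baseline, and the planned model uses a subject random effect and compound symmetry, so positive correlation is to be expected.

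**Conclusion.** The point holds as a mismatch between a stated figure and its stated inputs. As labelled, the inputs give 99.99% per bound and at least 99.7% for the decision rule, against a printed 84%. Either the power or the SD label is therefore misstated, and the documents do not show which.

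The as-labelled result needs no correlation assumption. It rests on a true effect of no more than 5 msec at each dose and timepoint and on t bounds approximating the mixed model. The 73% to 89% range is conditional on 7 msec being a per-treatment SD and on periods being independent given the subject. It is a sensitivity range, not an estimate of this trial's power. The correction is worth making because the replacement threshold relies on this sentence; it gives no reason to change the design.

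**What to change.** Keep 72 subjects and the decision rule. Restate the power sentence identically in Protocol 11.2 and SAP section 5, naming the formula and the number of bounds covered.

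- **If 7 msec is the SD of ΔΔQTcF, as labelled:** state that, with 56 evaluable subjects and a true effect of no more than 5 msec at any dose and timepoint, power is above 99% that all 18 one-sided 95% upper bounds lie below 10 msec (paired calculation).
- **If 7 msec is the per-period SD of ΔQTcF:** correct the label, give the implied SD of ΔΔQTcF (about 9.9 msec if periods are independent given the subject), and restate the power for all 18 bounds with the assumed correlation.

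The cost is one or two sentences in each document. Enrolment, endpoint and analysis are unchanged.
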